**1.I.d. Sample and Ascertainment**

Sample. A sample of n = 80 male and female adolescents and young adults with ASD will be enrolled. The expected male to female ratio is 4:1, based on current prevalence estimates of diagnosed ASD. With a conservative estimate of 25% attrition, we would achieve a final sample size of 60. Pitt will enroll 50 participants, and VT will enroll 30 (due to budget restrictions and population access).

**Figure 6.** RCT Design

Inclusion criteria consist of: (1) an ASD diagnosis, based on expert clinical opinion and supported by ADOS-2; (2) age 14-21 years; (3) Verbal IQ  $\geq$  80; (4) fluency in English; (5) a parent available and willing to participate; (6) evidence of at least an average degree of ER impairment for ASD (T-score of 45 or higher or 0.5 SD below the mean; on the Emotion Dysregulation Inventory Reactivity Short Form); and (7) medications are permitted but must be stable for 4 weeks with no planned changes.

Exclusion criteria consist of: (1) Current suicidality or homicidality that warrants more immediate care; (2) active psychosis; (3) Receiving concurrent psychotherapy treatment for emotional issues (i.e., depression, anxiety, anger) that overlaps with the current study.

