Randomization. Participants will be randomly assigned to EASE or ACC once eligibility is confirmed, by a data manager independent from the PIs and clinical team. Randomization algorithms have been created by the study statistician, independent of the PIs. Randomization will be done to ensure equal numbers of EASE and ACC at each site. Group assignment will be communicated to the PIs and assigned study clinician, who will then inform the participant. Site PI's ([name] and [name]) will closely monitor screening and randomization procedures and, should difficulties (e.g., more withdrawals from ACC than active) arise, they will be addressed immediately with the Data Safety and Monitoring Board.

Therapist training: At the start of the RCT, all therapists will convene for a training meeting for both treatments, on site at Pitt. The PIs will provide the theoretical background and didactic training, including live and video (from open pilot) demonstration of specific strategies. Study therapists must observe each recorded session (from open trial) before delivering that session with a study participant. In addition, every session of the first case of every therapist will be observed for integrity and training purposes by the respective site PI.

'Blind' maintenance: All Independent Evaluators will be 'blind,' or naive, to treatment assignment, and they will instruct participants not to reveal what intervention that they are receiving during the course of the procedures. Meetings with the independent raters will be conducted in a different office than the therapy, and the therapists and PI's will not be involved in outcome assessment. Regular assessments of treatment naive status will be conducted by the PI. When questions arise about possible need to break the blind (e.g., a potentially serious event becomes apparent during an assessment, but evaluator is not aware of treatment condition), [name] (Co-I at Pitt) will be the first contact. She will work with the PI's to determine how to proceed. If a participant breaks the blind, we will get another rater.

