### Characterization:

ASD and IQ inclusion criteria will be confirmed by: (1) the Autism Diagnostic Observation Schedule – Second Edition (ADOS-2), a semi-structured, standardized assessment that elicits behaviors relevant to the diagnosis of ASD administered by a research reliable ADOS tester (Lord et al. 2012), and (2) the Wechsler Abbreviated Scale of Intelligence, Second Edition (WASI-2; Wechsler et al., 2011), a reliable and valid measure of intelligence based on four subtests provide a brief, general estimate of functioning and a verbal IQ.

Measures with well-established psychometrics in ASD will be administered to quantify characteristics that may be related to ER and treatment response, including: (1): A subset from the Delis-Kaplan Executive Function System (D-KEFS; Delis et al., 2001) executive functioning battery including the Sorting task, which assesses conceptual reasoning and problem-solving, and the Color-Word Interference task, which assesses inhibitory control; (2) The 12-item Intolerance of Uncertainty Scale (IUS-12) which measures inhibitory and prospective anxiety (Boulter et al., 2014; Maisel et al., 2016); (3) The Social Responsiveness Scale, 2nd Edition (SRS-2) as a measure of ASD symptom severity, including specific subscales designed to assess treatment effects (Constantino et al., 2004; Constantino & Gruber, 2012); and (4) a well-validated and non-invasive self-report measure of puberty, the Pubertal Development Scale (PDS; Carskadon & Acebo, 1993).

Prior to treatment, caregivers and participants with ASD will separately complete a Needs Assessment, which was developed specifically for EASE to inform case conceptualization. It is a 19-item questionnaire that asked the rater to provide ratings of difficulty, on a 1-10 scale, for situations related to ER and socialization, as well as qualitative descriptions for any relevant items.

Information on Medications and Other Treatments will collected at each time point by parent report. We gather medication data by medication class. The parent report form also gathers information about non-pharmacological treatments (e.g., social skills training) by answering yes or not to a common list of interventions as well as an option to add open-ended additional information. Information is gathered on any changes in the past 4 weeks for all medications and psychosocial interventions endorsed.

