**General analytic approach.** Data will be analyzed based on CONSORT recommendations using intent-to-treat analyses with all participants who receive any exposure to their respective treatment condition. General linear models (analysis of variance [ANOVA] mixed models) will evaluate the differential trajectories of change between participants treated with EASE and ACC, after adjusting for demographic, medication, and other treatment confounders. It is *hypothesized* that participants who receive EASE will demonstrate significant differential improvements in ER, psychiatric symptoms, problem behavior, and functional impairments compared to the ACC. In addition, it is *hypothesized* that participants who receive EASE will maintain their gains at 3 months post-treatment compared to those treated with ACC. Exploratory analyses will also examine whether ER and mindfulness serve as mechanisms of change using a mediator analytic framework.

Because our population of interest is, by definition, vulnerable and their symptoms rapidly fluctuating, we believe it is insufficient to employ a traditional pre-post design for determination of treatment impact. For instance, a client might be responding well to treatment but then face the start of the school year immediately before the last session and experience heightened dysregulation; an analytic design that does not consider this will yield results that do not fully capture the pattern of growth. As such, we have refined our data collection procedures to include assessment of ER data at every session, which allows us to track our theorized mechanism of change in a nuanced way. We have also considered this issue in our analytic plan. After first utilizing traditional mixed model group comparisons of change, a more sophisticated analysis will be conducted using hierarchical linear models (HLM), which is also known as multilevel growth modeling (Raudenbush & Bryk, 2002). HLM casts the changes as the growth trajectories over time and allows us to examine the average amount of change, the amount of individual differences, and the correlates of changes between groups.

**Medication effects.** While randomization procedures should ensure comparable medication usage between treatment groups, given the modest sample size, differences in medication usage will be explicitly examined between treatment groups, and statistically controlled for in efficacy analyses if necessary.

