### **Statistical Analyses by Aim**

#### **Aim 1 (Primary Outcome): Show that EASE improves emotion regulation.**

First, to test the main effects of EASE on impaired ER (Hyp 1a) and maladaptive ER strategy use (Hyp 1b), we will employ linear mixed-effects models, with an auto-regressive error structure most appropriate to longitudinal data, allowing model intercepts and longitudinal trajectories to vary across subjects. Significant treatment by time interactions showing differences in linear rates of change in EDI Reactivity (Hyp 1a) and RSQ Involuntary and Voluntary Engagement scores (Hyp 1b) will be the effects of interest in these models. All mixed-effects models will control for potential demographic and medication confounds by including age, gender, IQ, and medication information as model covariates. This will be followed by modeling of growth trajectories between groups via HLM, also controlling for relevant potential confounds, using weekly data for Hyp 1a (EDI), and pre, mid, and post-treatment data for Hyp 1b (RSQ).

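### Arms are balanced within site, but no analysis model includes site: a small, avoidable loss of precision, with a minor medication wording conflict to tidy alongside it

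*Combined protocol and SAP*

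**What the plan says.** **Design.** Section 1.I.d (Randomization) states: "Randomization will be done to ensure equal numbers of EASE and ACC at each site". The Sample paragraph of the same section gives the site sizes: "Pitt will enroll 50 participants, and VT will enroll 30".

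**Models.** Under Aim 1 in Statistical Analyses by Aim, the tested effects are "Significant treatment by time interactions showing differences in linear rates of change". All mixed-effects models control for confounds by "including age, gender, IQ, and medication information as model covariates". The follow-up HLM refers to confounds in general terms, without a list. Aim 2 follows the Aim 1 approach, Aim 3 again uses mixed models and HLM, and Aim 4 mentions confounds without naming them. Site does not appear as a fixed effect, random effect or stratum anywhere in section 1.J.a or the by-aim analyses.

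**Medication.** The General analytic approach paragraph compares the arms "after adjusting for demographic, medication, and other treatment confounders", with no condition. The Medication effects paragraph says that "differences in medication usage will be explicitly examined between treatment groups, and statistically controlled for in efficacy analyses if necessary". Under Characterization, "Information on Medications and Other Treatments will collected at each time point by parent report". Entry requires that "medications are permitted but must be stable for 4 weeks with no planned changes". Section 1.K.a expects medication changes during the study and assigns them to a later look at their association with response.

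**The concern.** When arms are balanced on a factor by design, the analysis should normally include that factor. Otherwise the between-site spread stays in the residual variance, although it cancels from the treatment contrast. The reported standard error is then too large for the design actually used, and the test rejects too rarely under the null and under the alternative.

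The tested effect is a difference in rates of change. A constant level difference between sites is therefore mostly absorbed by the random intercepts. The term that matters is site-by-time: whether participants at one site change faster than those at the other. The documents give some reason to allow for this. Section 1.I.d describes recruitment at Pitt partly from a specialised psychiatric inpatient unit after discharge, and at VT from a clinic waiting list and registries.

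The medication wording raises a smaller, separate point. Two statements adjust always and one adjusts only after looking at the arms, with no criterion given. None of them ties medication to a time point.

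**Working it through.** The plan states no figure for site, so there is nothing to reproduce. The size has to be shown over assumed site differences. Two-sided alpha of 0.05 is also an assumption, as the documents do not state one.

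**1. Closed form for site.** Inputs: n=80 split 50/30 (section 1.I.d), so p = 30/80 = 0.375 and p(1−p) = 0.234. Take each participant's change, with within-site SD 1, and let the sites differ by d SD in mean change. With arms balanced in site:

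- True variance of the treatment contrast: 4/n, because the site difference cancels.
- Variance reported without site: (4/n)(1 + 0.234d²).
- SE ratio, with site over without: 1/√(1 + 0.234d²).
- Type I error without site: 2[1 − Φ(1.96/ratio)].

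At d=0.5: 1/√(1 + 0.0586) = 0.972; 1.96/0.972 = 2.017; type I error = 0.044.

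| Site difference in change (SD) | SE ratio, formula | SE ratio, simulated | Type I without site, formula | Type I without site, simulated (n=80) |
|---|---|---|---|---|
| 0 | 1.000 | 1.000 | 0.050 | 0.050 |
| 0.2 | 0.995 | 0.995 | 0.049 | 0.049 |
| 0.5 | 0.972 | 0.971 | 0.044 | 0.044 |
| 0.8 | 0.933 | 0.931 | 0.036 | 0.035 |

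The simulations used 100,000 replicates. The mean null estimate stayed within 0.0013 of zero, so there is no bias.

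**2. Power at n=60** (25% attrition, section 1.I.d; simulated as 38/22), for an assumed treatment effect of 0.7 SD. The SE is √(4/60) = 0.258, so 0.7/0.258 = 2.711. The normal approximation gives Φ(2.711 − 1.96) = 0.774 with site, and at d=0.5 Φ(2.711 − 2.016) = 0.756 without it, a gap of 1.7 points before rounding. Simulated power without site at d = 0, 0.2, 0.5, 0.8 is 0.759, 0.756, 0.742, 0.713. With site it is 0.759 to 0.761 throughout.

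**3. A model of the planned type.** REML fit, three waves, random intercept and slope, autoregressive residual with correlation 0.2, n=80, 25% dropout, 400 replicates. SE ratios at d = 0, 0.5, 0.8:

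- Site main effect only: 1.001, 0.998, 0.997.
- Site plus site-by-time: 1.002, 0.972, 0.934.

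The gain therefore comes from site-by-time.

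**4. CGI-I responder model** (logistic, n=80, 20,000 replicates, arm log-odds 1.25). At site log-odds 0, 0.5, 1.0, 1.5, power without site is 0.799, 0.794, 0.758, 0.713; with site it is 0.799, 0.795, 0.765, 0.741. Type I error without site is 0.053, 0.053, 0.045, 0.037; with site it is 0.054, 0.055, 0.052, 0.051.

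**5. Medication rules compared.** Baseline medication (60% medicated, assumed) entered as a main effect is constant over time, so in complete balanced data it cannot move the treatment-by-time estimate. The difference between adjusting and not adjusting is 0.000 SD. With 25% dropout it averages 0.004 SD, with a 95th percentile of 0.012 SD.

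**The case against.** The strongest reply on site is that the documents contain no evidence of different rates of change at the two sites, section 1.M.a aims for equivalent implementation across sites, and the gain is at most about 3% in the standard error over the plausible range. The 0.8 SD case would exceed the whole pilot pre-post change on EDI Reactivity (0.73, the pilot effect-size table in section 1.F). This stands as a limit on size. It does not argue against a term that costs almost nothing and matches the randomisation. The open references to confounds in the HLM and mediation text could admit site, but they do not pre-specify it.

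A reader might infer that omitting site biases the treatment effect or invalidates the test. It does not: within-site balance removes the site difference from the contrast, and the error rate moves below 0.05.

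On medication, a reader might infer that the two rules would yield materially different results. The conflict is narrower than that. The Aim 1 text and the General analytic approach agree on unconditional adjustment, and only the Medication effects sentence departs. Differences of 0.02 to 0.07 SD on average (95th percentile 0.06 to 0.19, centred on zero) require a medication-by-time term, which the plan does not specify.

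A reader might also infer that medication recorded after randomisation will be a covariate. The text does not say so, and three things favour baseline: the stability rule at entry, the argument that randomisation should make medication use comparable, and the separate role that section 1.K.a gives to later changes.

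**Conclusion.** The point holds as a free improvement in precision. Site is balanced by design and absent from every analysis model. There is no bias and no type I error inflation. For assumed site differences of 0 to 0.5 SD in change, the standard error would be 0 to 3% smaller with site-by-time, and power at n=60 about 0 to 2 points higher. For CGI-I the gain is negligible unless the sites differ strongly.

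The medication wording is a pre-specification clarification. For the longitudinal contrast with medication as a main effect, it changes the estimate by 0.000 to 0.004 SD.

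The reading of the text is firm. The magnitudes rest on assumed site and medication effects. The mixed-model simulation used three waves, so the weekly EDI growth model was not simulated directly. The effect of the medication choice in the CGI-I model was not quantified.

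**What to change.** 1. Add site and site-by-time as fixed effects to the Aim 1-3 longitudinal models, both the mixed models and the HLM.
2. Add site to the CGI-I responder model, and note that the odds ratio is then conditional on site.
3. Remove the condition at the end of the Medication effects sentence. Let one fixed covariate list apply to the mixed models and the HLM, with the general references to confounds pointing to that list.
4. State that medication means pre-randomisation status. Keep on-study changes for the separate analysis in section 1.K.a.

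**Cost.** Wording only, since all the variables are already collected. Site uses two degrees of freedom in the longitudinal models and one in the CGI-I model. If the sites do not differ, the SE ratio is 1.000 in complete data and 1.002 with 25% dropout.

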#### **Aim 2 (Secondary Outcomes): Demonstrate that EASE results in decreased functional impairment and reduced psychiatric symptoms and problem behaviors.**

The test of secondary outcomes will mirror the approach used in Aim 1. To evaluate change in functional impairment via CGI-I (Hyp 2a), we will create a dichotomous variable of responder = 1 and non-responder = 0. This is consistent with convention for use of the CGI-I in both psychosocial and drug treatment studies, such that 1 and 2 codes (‘very much’ and ‘much improved’, respectively) are considered responders and all others are non-responders. The other primary outcome of interest for Hyp 2b will be CAFAS scores. For Hyp 2b (psychiatric symptoms and problem behaviors), we will focus first on the BPRS as this is our most stringent and ‘blinded’ test, followed by ABC-I and PROMIS depression and anxiety.

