|---------------------------|------------------------------|----------|-------------------------------|----------|----------|----------|
| Functional Impairment     | CGI-Improvement              | 12       | -1.75 (.62)*                  | 2.81     | -9.75    | <.001    |
| Impaired ER               | EDI-Reactivity theta score   | 11       | -.49 (.67)                    | .73      | -2.40    | .037     |
| Maladaptive ER strategies | RSQ – Involuntary engagement | 11       | -11.46 (4.30)                 | 2.67     | -8.84    | <.001    |
| Depression                | PROMIS-Depression            | 11       | -7.27 (8.26)                  | .88      | -2.92    | .015     |
| Problem Behavior          | ABC-Irritability             | 11       | -5.73 (7.25)                  | .79      | -2.62    | .026     |
| Anxiety                   | PROMIS-Anxiety               | 11       | -4.46 (10.85)                 | .41      | -0.98    | .203     |

**Note.** \*For CGI-I, value represents mean change from 4, which equals no improvement; Parent report data shown

**Figure 3.** Illustrative examples of group mean change in key measures from baseline to post-treatment

Preliminary Efficacy evidence in young adults. Some of EASE’s content was informed by [name] & [name] (2017)’s ER-focused MBI open pilot that involved nine young adults with ASD age 18-25 who reported impaired ER (no cutoff on ER impairment was used). The baseline CGI-Severity scores covered the same range as the adolescent sample, though the adult sample was slightly less impaired, with a mean baseline severity (CGI-S) of 3.67 (*SD* = .71). The CGI-Improvement scores were similar to the EASE adolescent sample (2-3; *M*= 2.67; *SD*= .50). Treatment satisfaction was acceptable (*M*= 8.13; scale 1-10). In addition, seven of the nine participants had reliable improvement in impulse control, access to ER strategies, or emotional acceptance as measured on the Difficulty in Emotion Regulation Scale (Gratz & Roemer, 2004). While these results are promising, they are limited by the absence of a control group and lack of a required threshold for ER impairment to be enrolled in the study.

**Figure 4.** Individual and Mean Changes in DERS subscales

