### **Aim 2 (Secondary Outcomes): Demonstrate that EASE results in decreased functional impairment and reduced psychiatric symptoms and problem behaviors.**

- ❑ H2a: Participants in the EASE group will demonstrate significantly decreased functional impairment after treatment, relative to the ACC group.
- ❑ H2b: Following treatment, participants in the EASE group will show significantly greater reductions in psychiatric symptoms and problem behaviors relative to the ACC group, including depression, aggression/problem behavior, and anxiety.

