### Secondary Outcome Measures.

[figure not shown]
**Functional/Adaptive Outcome Measures:** Our secondary functional outcome measures include: (1) The CGI, and (2) the CAFAS, both completed by a blind rater at pre- and post-treatment, and follow-up.

**Clinical Global Impression** (CGI; Guy, 1976). The CGI is comprised of 2 scales: Severity (CGI-S) and Improvement (CGI-I), each rated on a 7-point scale. The CGI-I scale was designed to measure overall symptomatic change as compared to baseline. Scores range from 1 (Very Much Improved) to 4 (Unchanged) to 7 (Very Much Worse). The CGI-I has been used in many studies over the past 3 decades, including clinical trials of treatments for ASD (e.g., RUPP, 2002). In this study, the CGI-I is used as a categorical (responder vs. non-responder) outcome measure, and will assess global functioning (including functioning in school, activities of daily living, social activities, and home). In our open trial to pilot EASE, we successfully trained three independent raters to reliably assign CGI scores and established inter-rater agreement as well, cross-site.

**Child and Adolescent Functional Assessment** (CAFAS; Hodges, 2000). The CAFAS evaluates level of impairment in day-to-day functioning. It has over 20 years of research to support its sensitivity to change and has been applied in child welfare, juvenile justice, mental health, and school systems to identify level of functioning and needs. CAFAS domains include: School, Home, Community, Behavior Towards Others, Moods/emotions, Self Harm, Substance Use, and Thinking (assessing irrational thinking). The CAFAS has been widely used, including with samples that involved children with ASD (e.g., Bishop-Fitzpatrick et al., 2015).

**Psychiatric Symptoms/Problem Behavior:** Our primary measure of psychiatric symptoms and problem behavior will be the BPRS completed by a blind rater at pre, post-, and follow-up time points. In addition, we have several parent, self, and other reporter questionnaires of specific symptoms and problem behaviors that will be completed to allow tests of convergence across multiple reporters as well as to provide the possibility to evaluate composites via structural equation modeling, depending on the primary results.

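### Aim 2 borrows Aim 1's treatment-by-time mixed model, which cannot be estimated for the CGI-I responder outcome as written and is less precise than it need be for CAFAS and BPRS

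*Combined protocol and SAP*

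**What the plan says.** Statistical Analyses by Aim, Aim 2, gives one general rule: "The test of secondary outcomes will mirror the approach used in Aim 1". Under Aim 1 that approach is a linear mixed model with autoregressive errors and subject-specific intercepts and trajectories. The effect of interest is the treatment-by-time interaction, and the covariates are age, gender, IQ and medication. The outcome's own baseline value is not listed. The Aim 3 text confirms that the Aim 1 and Aim 2 hypotheses are tested with linear mixed models, and it brings the 3-month follow-up in at that stage.

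H2a is that EASE participants "will demonstrate significantly decreased functional impairment after treatment, relative to the ACC group". For CGI-I, Aim 2 adds that "we will create a dichotomous variable of responder = 1 and non-responder = 0". Secondary Outcome Measures says the same ("In this study, the CGI-I is used as a categorical (responder vs. non-responder) outcome measure") and defines the scale: "The CGI-I scale was designed to measure overall symptomatic change as compared to baseline". CGI and CAFAS are "both completed by a blind rater at pre- and post-treatment, and follow-up"; BPRS has the same three time points. CAFAS is listed there as a functional outcome, but the Aim 2 analysis text says "The other primary outcome of interest for Hyp 2b will be CAFAS scores".

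**The concern.** A treatment-by-time interaction needs an outcome measured at two or more times in the analysis window. CGI-I responder status does not meet that need by week 16. No binary model, link function, test of proportions or rule for a missing responder value is written. Baseline coding, model and missing-data handling would therefore be chosen after the data exist, for a hypothesis the plan calls confirmatory and places under Hochberg's correction.

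For CAFAS and BPRS the interaction can be estimated. With two waves and a free baseline mean in each arm it is the between-arm difference in change, which leaves unused precision that the baseline scores offer. The sample-size section says the main interest is in effects of at least moderate size, and that is where the loss matters.

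**Working it through.** **The plan's own figures.** No power or precision figure is given for CAFAS, BPRS or CGI-I responders. The nearest is 49 per group for d = 0.41 at 80% power. A one-sample (paired) t formula, two-sided 0.05, returns 49, and 4 for the CGI-I effect of 2.81. That CGI-I effect treats the score as continuous (the Table 2 note says "value represents mean change from 4, which equals no improvement"), so it does not plan the responder comparison.

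**Inputs from the documents.** 80 randomised in equal numbers, so 40 per arm; 25% attrition, so 60, or 30 per arm; two drop-outs among 20 pilot enrolments; analysis keeps all 80 (Intent to Treat section). **Assumptions.** Two-sided 0.05 before Hochberg; baseline to week-16 correlation rho of 0.3, 0.5, 0.7 with equal SDs; true difference 0.5 SD; 0, 8 or 20 of 80 missing at week 16 (80 × 2/20 = 8; 80 × 0.25 = 20 if all attrition falls by then).

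**CGI-I as written.** With only the week-16 wave, time is constant and group × time equals group. The design matrix (intercept, group, time, group × time) has rank 2 of 4, so there is no interaction to estimate.

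**CGI-I with everyone coded a non-responder at baseline** (not stated in the trial plan). The interaction estimate equals the week-16 risk difference. With the random slope of Aim 1, the zero-variance baseline leaves the likelihood unbounded: at residual variance 0.1, 0.01, 0.0001 and 0.000001 the log-likelihood is -22, 70, 254 and 439. With a random intercept only (its variance is estimated near 0), the zero baseline residuals dilute the pooled variance. Let m be the week-16 values per arm and SS their within-arm sum of squares:
- interaction variance = SS/(76 + 2m) × (2/40 + 2/m)
- week-16 variance = SS/(2m − 2) × 2/m
- SE ratio = √[(2m − 2)/(76 + 2m) × (1 + m/40)], giving 1.00, 0.95 and 0.86 at m = 40, 36 and 30.

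Example: 18/30 versus 9/30 gives SS = 7.2 + 6.3 = 13.5. The estimate is 0.30, with SE √(13.5/136 × 0.1167) = 0.108 against √(13.5/58 × 0.0667) = 0.125.

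Simulated type I error at responder rates of 0.30 and 0.45: about 0.054 and 0.055 with none missing, 0.065 and 0.075 with 8 missing, 0.098 and 0.091 with 20 missing. The week-16 t-test stays between 0.044 and 0.056.

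**CAFAS and BPRS.** Read Aim 2 as pre and week 16. In SD units, with 40 baselines and 30 week-16 values per arm:
- treatment-by-time variance = 2[(1 − rho²)/30 + (1 − rho)²/40]
- baseline-adjusted variance = 2(1 − rho²)/30

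| rho | interaction | adjusted | ratio | power, interaction | power, adjusted | 60 do the work of |
|---|---|---|---|---|---|---|
| 0.3 | 0.0852 | 0.0607 | 0.71 | 0.39 | 0.51 | 84 |
| 0.5 | 0.0625 | 0.0500 | 0.80 | 0.50 | 0.59 | 75 |
| 0.7 | 0.0385 | 0.0340 | 0.88 | 0.71 | 0.76 | 68 |

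Power is noncentral t at 0.5 SD (58 and 57 df). The last column is 60 divided by the ratio.

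**The case against.** The strongest reply on CGI-I is that a logistic model at week 16 is plainly what a responder variable implies, and that an analyst would notice a model that cannot be fitted. That may well be the intent. It still leaves the missing-data rule open: a participant without a week-16 CGI-I has no other value of that outcome in the Aim 2 window, although the plan says all 80 are analysed.

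A reader might infer that the plan will inflate type I error. The documents do not support that. The inflation needs a baseline coding the trial plan does not state and a random intercept in place of its varying trajectories, and it is negligible when nothing is missing. The Table 2 note describes pilot scoring, not a coding rule for the trial. A reader might also take the CGI-I test to be an interaction between post-treatment and follow-up, which would have almost no power against a sustained effect. That is not the plan either: follow-up enters under Aim 3, and H2a concerns the end of treatment.

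On CAFAS and BPRS, it is fair to say that the planned test is unbiased, that these are secondary outcomes, and that rho is not in the documents. It is also fair that complete-case ratios of (1 + rho)/2, or 0.65, 0.75 and 0.85, would overstate the gain, because the mixed model keeps the baselines of participants lost by week 16. The smaller gains in the table already allow for this. A mixed model with a common baseline mean would recover the precision, but none is stated.

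**Conclusion.** The concern stands in two parts of different weight. For CGI-I, the stated rule cannot be applied and no test of H2a on that measure is specified. This follows from the text and needs no assumption. The type I figures, up to 0.09 to 0.10 with 20 of 80 missing, show only what one unstated rescue would do.

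For CAFAS and BPRS, the planned interaction is valid but gives up about 12, 9 and 5 points of power at rho 0.3, 0.5 and 0.7. That rests on the assumed 0.5 SD difference, on 10 per arm lost by week 16, and on reading Aim 2 as pre and week 16. It is a loss of power, not bias, and it fades at high rho: the variance ratio is 0.92 at rho 0.8. The hypothesis label on CAFAS is a minor inconsistency. Nothing is claimed here about ABC-I, PROMIS or H3a. The change should be made before unblinding.

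**What to change.** 1. State that H2a on CGI-I is tested by the between-arm contrast in week-16 responders, using logistic regression on arm plus the plan's covariates (age, gender, IQ, medication). The Wald test of arm is the test; report the standardised risk difference from the same fit. For a missing week-16 CGI-I, use multiple imputation that includes arm, all analysis covariates, baseline CGI-S and weekly EDI, with missing counted as non-responder as a sensitivity analysis. Weekly EDI is parent-reported while CGI-I is blind-rated, which is one more reason to show both.
2. For CAFAS and BPRS, state that the Aim 2 window is pre and week 16. Test the week-16 arm contrast in a categorical-time model with a common baseline mean, unstructured covariance and the same covariates. With complete data this matches baseline-adjusted ANCOVA, and it keeps participants who lack week 16.
3. Correct the hypothesis label on CAFAS in the Aim 2 analysis text to agree with Secondary Outcome Measures.

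The cost is SAP wording and a little more analysis; every variable is already collected. The adjusted logistic test has a small price. At N = 60 its simulated type I error is about 0.056 to 0.058, and its power at an assumed 30% versus 60% is about 0.63, against 0.66 for the unadjusted comparison.
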